6.3.3 Retreatment of patients experiencing DLT

Patients experiencing DLT during the DLT assessment period will not receive additional trial treatment unless all the following conditions are met:

- The DLT has resolved to at least Grade 1 or returned to baseline with appropriate treatment (e.g., anti-emetics) or with a delay in trial treatment dosing.
- The DLT is not expected to recur based on an intervention such as prophylactic use of appropriate treatment (e.g., prophylactic anti-emetics), or dose reduction.
- Continued administration of trial treatment is considered to be in the patient's best interest based on the opinion of the investigator and the sponsor.

For the combination mFOLFIRINOX + BNT321, if a DLT is considered clearly related to a specific drug, the patient may continue with the remaining trial treatment if considered in the patient's best interest by the investigator and the sponsor.

6.3.4 Mitigation plans for BNT321 IRRs

IRRs are a general risk to be considered for any new compound administered IV irrelevant of its mechanism of action. An IRR is typically of immediate onset during or after the compound's administration. The risk of IRR cannot be excluded for BNT321.

All patients should be pre-medicated prior to BNT321 administration. Premedication to prevent IRR should be administered at the investigator's discretion according to local guidelines and recommendations of the SRC, see Section 6.9.3.

The following treatment guidelines are provided below for patients who experience an IRR associated with administration of BNT321 treatment (Table 13). The Medical Monitor should be contacted with any questions regarding these guidelines.

Table 13: Treatment guidelines for patients who experience a BNT321-related IRR

Grade	Definition	Treatment guideline
1	Mild transient reaction; infusion interruption not indicated; intervention not indicated.	Monitor for at least 2 hours after end of infusion; provide patient instructions and prophylactic medications at discharge as appropriate.
2	Therapy or infusion interruption indicated but responds promptly to symptomatic treatment.	Infusion may be restarted once following a minimal 60-minute delay. A second infusion interruption requires discontinuation of BNT321 administration. Administration of medications (e.g., antihistamines, steroids, NSAIDS and IV fluids etc.) as appropriate; monitor in clinic for at least 2 hours after completion of infusion; provide prophylactic medications as appropriate for subsequent BNT321 doses.

Page 64 of 127 Version: 2.0 Date: 22 JAN 2024

Grade	Definition	Treatment guideline
3	Prolonged (e.g., not rapidly responsive to symptomatic medication and/or brief interruption of infusion); recurrence of symptoms following initial improvement, hospitalization indicated for clinical sequelae.	Administration of medications (e.g., anti-histamines, steroids, NSAIDS and IV fluids etc.) as appropriate; hospitalization for medical care and observation; discontinue BNT321 permanently.
4	Life-threatening consequences; urgent intervention indicated.	Hospitalization for urgent medical treatment; discontinue BNT321 permanently.

Abbreviations: IV = intravenous; NSAIDS = nonsteroidal anti-inflammatory drugs.

NOTE: For Grade 2 IRR prophylactic medications for subsequent BNT321 doses may include the institution of a prophylactic oral steroid regimen (20 mg dexamethasone 12 hours prior; 20 mg dexamethasone 6 hours prior; 6 mg dexamethasone twice daily for 3 days) at the investigator's discretion.

- All premedications must be reported on the Prior/Concomitant Medication electronic case report form (eCRF).
- IRR Grade ≥3 is an adverse event of special interest (AESI) (see Section 8.4.8).

6.3.5 Safety stopping rules

The following are safety stopping criteria for implementation of the Phase II part of the study only:

- Any death possibly related to the BNT321 within 30 days of receiving IMP.
- If during treatment, more than 33% of trial patients develop AEs meeting the DLT criteria, the trial cohort shall be paused pending a safety evaluation by the IDMC and sponsor.
- Any safety finding assessed as related to BNT321 that, in the opinion of the IDMC, contraindicates further dosing of trial patients.

These rules a priori will be followed by the SRC to take the temporary stopping decisions before final decision is implemented (e.g. permanent discontinuation, dose reduction of a treatment in the combination or adaptation of a monitoring plan)

Individual patients in all phases of the study will be discontinued from the study according to the safety stopping criteria detailed in Section 7.2.

6.4 Actions in case of overdose or errors in drug administration

For a definition of an overdose, see the subsection "AEs associated with an overdose or error in drug administration" in Section 10.4.1.3.3.

Overdose *per se* will not be reported as an AE but must be recorded on the relevant eCRF page.

Page 65 of 127 Version: 2.0 Date: 22 JAN 2024

The sponsor does not recommend specific treatment for an overdose.

In the event of an overdose or an error in drug administration, the investigator should:

- Contact the sponsor's Medical Monitor immediately.
- Closely monitor the trial patient for any AE/SAE and laboratory abnormalities (at least 28 days).
- Document the quantity of the excess dose as well as the duration of the overdose in the eCRF.

Decisions regarding dose interruptions or modifications will be made by the investigator in consultation with the sponsor's Medical Monitor based on the clinical evaluation of the trial patient.

6.5 Preparation/handling/storage/accountability

The investigator or designee must confirm appropriate temperature conditions have been maintained during transit for all trial treatment received and any discrepancies are reported and resolved before use of the trial treatment.

Only patients enrolled in the trial may receive trial treatment and only authorized site personnel may supply or administer trial treatment. All trial treatment must be stored in a secure, environmentally controlled, and monitored (manual or automated) area in accordance with the labeled storage conditions with access limited to the investigator and authorized site personnel.

The investigator, site, or the head of the site (where applicable) is responsible for trial treatment accountability, reconciliation, and record maintenance (i.e., receipt, reconciliation, and final disposition records).

Any non-compliance with the provided storage conditions should be reported to the sponsor upon discovery along with any actions taken. Once non-compliance is identified, the trial treatment must be quarantined and not used until the sponsor provides permission to use/discard/return the trial treatment.

Further guidance and information for handling, administration, and final disposition of trial drug are provided in the Pharmacy Manual.

6.5.1 BNT321

BNT321 for injection is stored at -15°C to -25°C and is provided as a single-use vial containing 8.0 mL of sterile solution at 10 mg/mL in a buffer at pH 6.0, containing 25 mM histidine, 150 mM sucrose, 55 mM sodium chloride, and 0.02% polysorbate 80. BNT321 for injection is packaged in clear USP Type I borosilicate glass vials with 20 mm West 4432/5- stoppers (grey colored coated closures) and blue 20 mm flip-off seals.

Prior to infusion, BNT321 is diluted in normal saline to obtain a final concentration of less than 5 mg/mL. The administration apparatus must include a 0.2-micron inline filter. BNT321 must be administered within 24 hours of preparation.

Page 66 of 127 Version: 2.0 Date: 22 JAN 2024

6.5.2 mFOLFIRINOX

mFOLFIRINOX will be prepared and administered according to institutional standards, in compliance with the package insert for each drug or as SmPC.

Pre- and postmedications will be administered in compliance with the package insert for each drug and according to institutional standards. Patients with IRR should be treated according with the package insert for each drug and according to institutional standards.

6.6 Patient assignment, randomization, and blinding

6.6.1 Assignment

For the Phase I part of this trial, patients will be enrolled sequentially to dose cohorts using a 3+3 dose escalation design.

For the Phase II part of this trial, patients will be enrolled to treatment arms through randomization, as described in Section 6.6.2.

6.6.2 Randomization

For Phase II, part 2, patients will be randomized in a 1:1 fashion to one of two treatment arms, mFOLFIRINOX + BNT321 or mFOLFIRINOX alone. Randomization will be conducted in the trial's interactive web response system (IWRS) up to 3 days before Cycle 1 Day 1. Randomization will include stratifications to ensure balanced enrollment between the two arms for the following characteristics: tumor resection status (R0 vs R1) and tumor nodal status at resection (pN0 vs pN1).

6.6.3 Blinding/Unblinding

BNT321-01 Phase II, part 2 is a randomized, open-label trial. Potential bias in assigning patients to treatment groups will be reduced by randomization. For the conduct of this part of the trial, trial site personnel will be unblinded regarding treatment allocation.

Radiologists that assess the CT scans will be blinded to the trial treatment.

6.7 Trial treatment compliance

Patients will receive trial treatment directly from the investigator or a designee under medical supervision. The date and time of each dose administered must be recorded in the source documents and in the eCRF. The dose of trial treatment and patient identification number will be confirmed at the time of dosing by a member of the trial site personnel other than the person administering the trial treatment. See Section 6.4 for guidance on the treatment of overdose or errors in drug administration.

6.8 Access to trial treatment after the end of the trial

The sponsor does not plan any extension studies or possibilities for continued access to trial treatment after completion of the trial.

Page 67 of 127 Version: 2.0 Date: 22 JAN 2024

6.9 Concomitant therapy

Prior treatments are any medications and non-drug therapies used by the patient up to 21 days before trial treatment initiation on Cycle 1 Day 1. Concomitant medications and therapies are any medication (e.g., prescription drugs, over-the-counter drugs, vaccines, herbal or homeopathic remedies, or nutritional supplements) used by a patient in addition to protocol-mandated treatment (including prophylactic treatment after BNT321 administration and medications as a result of an AE).

6.9.1 Prohibited medication during the trial

Patients must be instructed not to take any medications, including over-the-counter products, without first consulting with the investigator.

The following medications and substances are prohibited during the trial:

- Any other investigational therapy.
- Antineoplastic systemic chemotherapy or biological therapy.
- Steroid treatment for any other purpose except to manage significant trial-related toxicity including to modulate symptoms of an IRR. Chronic systemic immunosuppressive corticosteroid doses (i.e., more than 10 mg/day prednisone or its equivalent) is prohibited. Steroid premedication may only be used prophylactically for chemotherapy-related toxicities when clinically indicated in the opinion of the investigator or per protocol Section 6.9.3.
- No dietary supplements are allowed during the trial period (except for multivitamins, vitamin D, calcium, and supplements in prevention of weight loss). The use of traditional/herbal medicines is not permitted.
- Strong CYP3A4 inducers, inhibitors, and UDP glucuronosyltransferase family 1
 member A1 (UGT1A1) inhibitors should be discontinued for at least 2 weeks prior
 to initiation of mFOLFIRINOX therapy. The sponsor should be contacted if the
 primary investigator feels there are no therapeutic alternatives.
- Live or live attenuated vaccines should be avoided during irinotecan therapy and are exclusionary for the study if given within 3 weeks of the first dose of trial treatment.

If a patient receives any of these during the trial, the sponsor must be notified for determination of whether the patient may be permitted to continue on trial.

6.9.2 Permitted medication during the trial

Investigators may prescribe concomitant medications or treatments deemed necessary to provide adequate supportive care except for those medications identified as "prohibited" (Section 6.9.1). Administration of concomitant medications must be reported in the appropriate section of the eCRF.

Page 68 of 127 Version: 2.0 Date: 22 JAN 2024

- Granulocyte colony stimulating factor and other hematopoietic growth factors may be used in the management of acute toxicity (such as febrile neutropenia) or prophylactically, when clinically indicated at the investigator's discretion.
- Blood cell transfusion (RBC or platelet) is allowed if clinically indicated and must be reported in the concomitant procedures section of the eCRF.
- Systemic (oral or IV) steroid therapy ≤10 mg prednisone daily or its equivalent for an underlying condition (refer to Section 6.5.1).
- Replacement therapy (e.g., thyroxine, insulin, or physiologic corticosteroid replacement therapy for adrenal or pituitary insufficiency).
- Bisphosphonates (e.g., pamidronate, zoledronic acid, etc.) and denosumab.
- Paracetamol/acetaminophen, or acetylsalicylic acid/aspirin, at doses of less than 2 g/day, is permitted for use at any time during the trial.
- Multivitamins, vitamin D, calcium, and supplements in prevention of weight loss.

The Medical Monitor should be contacted if there are any questions regarding concomitant or prior therapy.

6.9.3 BNT321 premedication

Pre and postmedications will be provided to mitigate potential reactions to BNT321. The recommended dose is 8 mg of dexamethasone IV at least 30 minutes prior to infusion and 4 mg dexamethasone twice daily for 2 days following BNT321 administration. The investigator may gradually reduce this regimen as appropriate in those patients without clinical evidence of IRRs.

The SRC or IDMC may modify the prophylactic regimen during the course of the trial as appropriate.

6.9.4 Vaccination against COVID-19

It is generally assumed that cancer patients may be at an increased risk of severe COVID-19 due to immunosuppression that may result from both anticancer treatment and the malignancy itself (Cook et al. 2020, Dai et al. 2020, Liang et al. 2020). As for the entire population, immunization with COVID-19 vaccine reduces the likelihood of SARS-CoV-2 infection as well as intensity of disease in patients with cancer. Additionally, decreasing the likelihood of SARS-CoV-2 infection by vaccination against COVID-19 may allow better adherence to anticancer therapeutic regimens and in doing so potentially increase treatment efficacy. Based on the available non-clinical and clinical data, the sponsor considers that the potential benefits of vaccination against COVID-19 in patients with PDAC treated with BNT321 outweigh the anticipated risks.

The following recommendations are proposed to mitigate potential risks:

• Patients with prior vaccination against COVID-19 will only be allowed to enter this trial with a washout period of at least 7 d since the last COVID-19 vaccine dose.

Page 69 of 127 Version: 2.0 Date: 22 JAN 2024

- Patients who are already enrolled in this trial and still receiving trial treatment will
 only be allowed vaccination COVID-19 if it is ensured that there are at least 7 d
 between individual doses of COVID-19 vaccine and trial treatment.
- In terms of the risk/benefit of COVID-19 vaccination, the final decision for individual patients should be taken by the investigator in accordance with individual country guidance on vaccination in patients with active cancer.
- Patients treated with BNT321 should not be immunized directly prior to and during the trial with live attenuated vaccines, as per prohibited concomitant medication and patients are excluded from the study if they have received a live vaccine within 3 weeks prior to the first dose of trial treatment (see Section 6.9.1).

6.9.5 Recording concomitant medication during the trial

All concomitant medication permitted or prohibited (including over-the-counter or prescription medicines, vitamins, and/or herbal supplements) that the trial patient receives should be reported to the investigator and recorded on the Prior/Concomitant Medications eCRF along with:

- · Reason for use
- · Dates of administration including start and end dates
- Dosage information including dose and frequency

The trial Medical Monitor should be contacted if there are any questions regarding concomitant or prior therapy.

The start and stop dates and name of the concomitant medication during the trial will be recorded in the eCRF for the period defined in the SoA (Section 1.3).

7 DISCONTINUATION OF TRIAL TREATMENT AND PATIENT DISCONTINUATION/WITHDRAWAL

7.1 Discontinuation or pausing (temporary halting) of trial treatment

7.1.1 Permanent discontinuation of trial treatment

Patients permanently discontinued from trial treatment will not be discontinued from the trial (i.e., will continue with trial visits, and complete disease assessments and Survival FU Visits).

Administration of BNT321 will be discontinued in the event of any of the following:

- Discontinuation of BNT321 for abnormal liver function should be considered by the investigator when a patient meets one of the conditions outlined in Section 6.3.1 or if the investigator believes that it is in best interest of the patient;
- Recurrence of disease;

Page 70 of 127 Version: 2.0 Date: 22 JAN 2024

- Continued treatment is not considered to be in the patient's best interest in the opinion of the investigator;
- Unacceptable AE(s) considered related to mFOLFIRINOX or BNT321, despite addition of appropriate therapy to manage toxicities (see Section 6.3);
- Pregnancy;
- Withdrawal of consent by the patient;
- Significant patient non-compliance as determined by the clinical investigator;
- Termination of trial by the sponsor.

See the SoA (Section 1.3) for data to be collected at the time of trial treatment discontinuation and follow-up and for any further evaluations that need to be completed.

7.1.2 Pausing of trial treatment (temporary halting)

Details for withholding of mFOLFIRINOX and BNT321 therapy are provided in Section 6.3.

A pause of trial treatment may be caused by a failure in the trial treatment supply chain such that there is no trial treatment available.

See the SoA (Section 1.3) for data to be collected at the time of pausing trial treatment discontinuation and for any further evaluations that need to be completed.

7.1.3 Rechallenge

Parameters for retreatment of mFOLFIRINOX and BNT321 following regression of observed toxicities are outlined in Section 6.3.

Patients are not permitted to re-enter the trial following termination of trial treatments and completion of the EOT visit.

7.2 Patient discontinuation/withdrawal from the trial

A patient who has consented during any phase of the trial, who requests to discontinue receipt of trial treatment, will remain in the trial, and the patient must continue to be followed for protocol specified follow-up procedures. The only exception to this is when a patient specifically withdraws consent for further continuation in the trial.

A patient will be withdrawn from the trial at any time at their own request or discontinued from the trial at any time at the discretion of the investigator for safety, behavioral, compliance, or administrative reasons.

Reasons for patient discontinuation from the trial include the following:

- Lost to follow-up;
- Death;
- Withdrawal of content;
- Patient noncompliance;

Page 71 of 127 Version: 2.0 Date: 22 JAN 2024

- Investigator decision;
- Trial terminated (closure of all sites) by sponsor;
- Protocol deviation;
- Pregnancy.

See the SoA (Section 1.3) for data to be collected at the time of withdrawal/discontinuation from the trial and for any follow-up / further evaluations that need to be completed.

If discontinued from the trial, the patient will be permanently discontinued both from the trial and from the trial treatment at that time. In these cases, the sponsor will retain and continue to use any data collected before the permanent discontinuation.

If a patient withdraws from the trial, they may request destruction of any samples taken and not tested, and the investigator must document this in the site trial records.

Lack of completion of all or any of the withdrawal/early termination procedures will not be viewed as a protocol deviation as long as the patient's safety was preserved.

For guidance on premature termination or suspension of the whole trial, see Section 10.1.9.

Re-enrollment is not permitted following trial discontinuation.

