4 TRIAL DESIGN

4.1 Overall design

This trial is designed as a Phase I/randomized Phase II open-label trial of mFOLFIRINOX ± BNT321 for adjuvant therapy in PDAC patients post R0 or R1 resection.

Screening will occur ≤21 days prior to Cycle 1 Day 1. Patients will provide written informed consent prior to the performance of any screening-related procedures. Eligibility status will be determined and be provided to the physician that submitted the patient's tissue for testing. Medical history includes cancer history (including but not limited to, lifetime history of cancer, tumor characteristics such as mutation status, cancer-related somatic genomic alterations and germline status, prior non-cancer significant medical conditions for the 2 years prior to trial entry, other clinically relevant diseases, including tuberculosis, surgeries, use of alcohol and/or drugs abuse and reproductive status).

The Phase I, dose escalation part of this trial will be a limited evaluation of two planned BNT321 dose levels in combination with mFOLFIRINOX chemotherapy (24 weeks) followed by BNT321 monotherapy (24 weeks). Following determination of the combination recommended Phase II dose (RP2D), the Phase II (randomized treatment) part of this trial will be initiated as an open-label 2-arm evaluation of mFOLFIRINOX ± BNT321 (24 weeks) followed by BNT321 monotherapy (24 weeks) in the combination arm only to complete the adjuvant therapy course. Treatment cycles are every 2 weeks (14 days).

The primary endpoint for the Phase I part of this trial is characterization of the safety and RP2D of BNT321 in combination with mFOLFIRINOX. The primary endpoint for Phase II of this trial is to assess the efficacy of mFOLFIRINOX + BNT321 versus mFOLFIRINOX alone as adjuvant therapy in PDAC patients post R0 or R1 resection by DFS.

Safety monitoring assessments will be performed 28 days after the last dose of BNT321. Information on survival follow-up, new anticancer and cancer-related procedures will be collected for all patients via telephone calls, patient medical records, and/or clinic visits from BNT321 treatment discontinuation and approximately every 12 weeks until 5 years (unless the patient withdraws consent, or the sponsor terminates the trial).

The duration of the trial periods is given in Section 4.1.4.

Page 44 of 127 Version: 2.0 Date: 22 JAN 2024

The planned number of patients is given in Section 4.1.5.

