8.2.4 Survival follow-up

Following the safety follow-up visit, site staff will contact the patient every 3 months for 2 years and then every 6 months for the next 3 years or until the patient is lost to follow-up or dies. Survival follow-up will determine survival status and record if patients have taken any new anticancer treatments. This contact may be by telephone, E-Mail or other form of communication but must be documented in the source notes.

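### Section 7.2 lets the investigator remove a randomized patient from the trial, conflicts with 7.1.1, 8.4.5, 4.1, 8.2.4 and the schedule of activities, and leaves open whether DFS scans continue

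*Combined protocol and SAP*

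**What the plan says.** Section 7.1.1 deals with stopping treatment: "Patients permanently discontinued from trial treatment will not be discontinued from the trial". These patients go on with visits, disease assessments and survival follow-up. The reasons it lists for ending BNT321 include "Significant patient non-compliance as determined by the clinical investigator", unacceptable adverse events, the investigator's view of the patient's interest, and pregnancy. Section 8.4.5 also says that pregnancy ends trial treatment, and does not say that the patient leaves the trial.

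Section 7.2 starts in the same spirit. A patient "who requests to discontinue receipt of trial treatment, will remain in the trial", with withdrawal of consent as the sole exception. Its next paragraph lets the investigator discontinue a patient from the trial "at any time at the discretion of the investigator for safety, behavioral, compliance, or administrative reasons". The reasons that follow include noncompliance, investigator decision, protocol deviation and pregnancy. Such a patient leaves both trial and treatment, and 7.2 then speaks only of keeping data already collected. It refers to the schedule of activities for further evaluations. It adds: "Lack of completion of all or any of the withdrawal/early termination procedures will not be viewed as a protocol deviation", on condition that the patient's safety was maintained. Section 8.12 asks for one Early Termination Visit.

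Elsewhere follow-up is general. Section 4.1 has information collected "approximately every 12 weeks until 5 years (unless the patient withdraws consent, or the sponsor terminates the trial". Section 8.2.4 has contact continue "every 6 months for the next 3 years or until the patient is lost to follow-up or dies", and describes its content: "Survival follow-up will determine survival status and record if patients have taken any new anticancer treatments". Section 1.3 makes scans mandatory at 3-month and later 6-month intervals over 5 years. Footnote 6 of its Table 2 asks that every patient be contacted, or the records checked, for survival, progression and an imaging update.

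**The concern.** The same finding, such as noncompliance, can lead to full DFS follow-up under 7.1.1 or to exit from the trial under 7.2, depending on which section a site applies.

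Survival status is fairly well covered by 4.1, 8.2.4 and footnote 6, so for that endpoint the problem is mainly inconsistency. DFS is more exposed. Under 9.5.2 a recurrence counts for the primary endpoint when independent central radiology determines it. A telephone contact or record review cannot replace a scan that was not done.

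The primary analysis uses all randomized patients (9.4, 9.5.2), and the sample size assumes follow-up until a DFS event (9.3). Site staff know the allocation (6.6.3), and treatment lasts 48 weeks in one arm and 24 in the other (4.1.4), so exits could differ by arm. If they do, and removed patients differ in relapse risk, censoring them is informative. If they are instead carried as event-free without scans, unequal exit alone can bias the comparison. Censoring rules are left to the SAP; these can decide how missing scans are handled but cannot recover them.

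**Working it through.** **1. The passages side by side**

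| Reason | 7.1.1 | 7.2 |
|---|---|---|
| Non-compliance | treatment ends, patient stays in trial | may leave trial |
| Pregnancy | same (8.4.5 also ends treatment only) | may leave trial |
| Safety / unacceptable adverse events | same | may leave trial (close overlap) |
| Investigator's judgement | same | may leave trial (close overlap) |
| Protocol deviation, behavioral, administrative | not listed | may leave trial |
| Consent withdrawn, trial terminated | listed | listed; not in dispute |

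The 7.1.1 list is written for BNT321; the control arm has no list of its own. The sentence in 7.2 that keeps patients in the trial covers those who themselves ask to stop treatment, not investigator-initiated exit.

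**2. The plan's event count**

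Inputs from 9.3: HR 0.60, two-sided 5%, power 90%, 1:1. Schoenfeld: 4 × (1.960 + 1.282)² / (ln 0.60)² = 161.1, so 162, against 164 stated. Power at 164 events is 0.905. The figure reproduces to within 2 events; Section 9.2 is redacted, so any adjustment made there cannot be checked.

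**3. Illustration of the effect on the test**

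From the plan: 150 per arm, 24 months' accrual (taken as uniform), median DFS 21.6 months, 10% drop-out per year, analysis at 164 events. Assumed: no treatment effect; 10% of each arm has 1, 2 or 3 times the DFS hazard of the rest; removed patients all come from that group; exit is uniform over 0 to 11 months; the larger removal is in the combination arm. The test is an unstratified log-rank, with 40,000 simulated trials per scenario (standard error about 0.11 percentage points).

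Handling A censors at exit. Handling B stops scans but counts the patient as event-free until death. Handling C counts deaths and censors survivors at exit. B and C take mean survival after a DFS event as 33.7 months, chosen to match median DFS 21.6 and median OS 54.4 months (2.2.1).

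| Handling, removed | HR at ×1 / ×2 / ×3 | Two-sided error (%) |
|---|---|---|
| None removed | 1.00 / 1.00 / 1.00 | 5.0 / 4.9 / 4.4 |
| A, 10% vs 5% | 1.00 / 0.98 / 0.97 | 5.1 / 5.3 / 5.0 |
| A, 10% vs 0% | 1.00 / 0.96 / 0.94 | 5.2 / 5.7 / 6.4 |
| B, 10% vs 5% | 0.97 / 0.96 / 0.96 | 5.4 / 5.9 / 5.8 |
| B, 10% vs 0% | 0.93 / 0.91 / 0.91 | 7.6 / 9.2 / 8.9 |
| C, 10% vs 0% | 1.01 / 0.97 / 0.96 | 5.1 / 5.1 / 5.3 |

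- Balanced removal, 10% vs 10% at ×2: HR 1.00 with error 5.1% (A) and 5.3% (B).
- Few removals, 4% vs 2% at ×2 (20,000 trials): A gives HR 0.99 and 4.7%; B gives HR 0.98 and 5.0%.
- If removed patients have half the hazard, the direction reverses: A, 10% vs 0%, gives HR 1.05 and 6.1%.
- B depends on survival after recurrence. With a mean of 12 to 60 months, 10% vs 0% at ×2 gives HR 0.948 to 0.896 and error 6.3% to 10.4% (20,000 trials).

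**4. Effect on timing**

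The analysis is event-driven, so lost events mainly cost time. Under A at ×2, 164 events are reached on average 42.3 months after first randomization with no removal, 45.2 at 10% vs 0% (2.9 months later) and 48.8 at 10% vs 10% (6.5 months later).

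**The case against.** The strongest reply is that 7.1.1 and 7.2 have different jobs: one governs stopping treatment and the other leaving the trial. The 7.1.1 list also includes withdrawal of consent and termination of the trial, so a reader who infers that it marks reasons ending treatment only goes beyond the text. That stands. Only non-compliance and pregnancy match exactly across the two lists. The rule in 7.1.1 also protects patients whose treatment the investigator stops, as long as they are not removed from the trial.

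A reader might also infer that DFS imaging must stop on exit. The documents do not say so. Section 7.2 points to the schedule of activities, Section 1.3 makes scans mandatory for 5 years, footnote 6 covers all patients, and 4.1.4 has DFS status recorded throughout. What remains is that none of these addresses a patient already removed from the trial, while 7.2 mentions only earlier data. Nor does 7.2 excuse missed exit procedures without limit, since the sentence carries the safety condition.

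The larger error figures rest on harsh inputs. Ten percent against none means 15 of 150 patients against zero, all drawn from one risk group, on top of a 10% yearly drop-out that may already include them. Handling B is not specified anywhere. The nearest convention, for RFS in 9.5.3, censors at the last date known to be event-free. This too stands.

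The IDMC's review of primary endpoint data (10.1.5) and the contact steps before loss to follow-up (7.3) are useful, but neither tells a site whether to scan a removed patient.

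**Conclusion.** The conflict is real and should be corrected. As written, 7.2 allows centrally read DFS assessment to end for some randomized patients for reasons that elsewhere leave them under follow-up, and sites may apply the sections differently.

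The size and direction of any bias cannot be computed from the documents, which give no removal rates, no risk profile of removed patients and no censoring rules. Under the stated assumptions the effect is negligible when removals are balanced or few. It becomes noticeable only when removal is strongly unequal, especially if unscanned patients count as event-free. An error rate of 8% to 9% should not be read as the expected consequence; it needs both 10% against 0% removal and handling B.

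Two cross-references are separate, minor items. Section 6.3.5 refers to safety stopping criteria in 7.2, and 8.3.3 to QTc withdrawal criteria in Section 7; neither set is there. A reader might count these as further evidence of DFS bias, but they have no bearing on it.

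**What to change.** Reconcile 7.2 with 7.1.1, 8.4.5, 4.1, 8.2.4 and the schedule of activities by separating the end of trial treatment from the end of outcome follow-up. State in 7.2 that noncompliance, protocol deviation, investigator decision, safety reasons and pregnancy do not by themselves end collection of DFS and survival status. That collection ends only with withdrawal of consent, death, loss to follow-up, termination by the sponsor, or completion of scheduled follow-up. How disease status is assessed clinically in these patients is for the sponsor and the investigator.

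As a minor item, reconcile the cross-references in 6.3.5 and 8.3.3 with Section 7; which criteria apply is for the sponsor to decide.

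The cost is protocol wording, plus follow-up already on the schedule for the patients affected. The 300 patients and the 164-event target stay as they are.
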